## Appendix 5 – IMWG Renal Response Criteria and simplified renal response criteria

Criteria for the Definition of Renal Response to Antimyeloma Therapy		
Renal Response	Baseline eGFR, mL/min/1.73 m  *	Best eGFR Response mL/min/1.73 m 
Complete response	<50	≥60
Partial response	< 15	30-59
Minor response	<15 15-29	15-29 30-59

Abbreviations: CrCl, creatinine clearance; eGFR, estimate glomerular filtration rate.

\*eGFR is based on the Modification of Diet in Renal Disease formula, or the Chronic Kidney Disease Epidemiology Collaboration equation.

Simplified criteria Renal Response criteria
• Patients who presented with stage 5 RI (eGFR < 15 ml/min/1.73 m  ) should double their eGFR and improve to at least stage 4
• Patients with stage 4 (eGFR 15-29 ml/min/1.73 m  ), increase their eGFR by at least 50% and improve to at least stage 3 (GFR ≥ 60 mL/min/1.73 m  )
• Patients with stage 3 (eGFR 30-59 ml/min/1.73 m  ), increase their eGFR by at least 50% and improve to at least stage 2 (GFR ≥ 60 mL/min/1.73 m  )

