6.1.1 Study Population & Number of participating Sites

About 38 patients will be enrolled. The study will be conducted at approximately 5 sites located in Greece and approximately 2 sites located in Italy.

Main inclusion criteria are the following:

1. Males and females at least 18 years of age.
2. Voluntary written informed consent before performance of any study-related procedure
3. Myeloma requiring systemic therapy
4. Myeloma relapsing after, or refractory to, two or more different prior therapies, including immunomodulatory agents, proteasome inhibitors and chemotherapy with alkylating agents. Subject must have documented relapsed or refractory multiple myeloma as defined by the criteria below:
 - c) Monoclonal plasma cells in bone marrow $\geq 10\%$ or presence of a biopsy proven plasmacytoma.
 - d) Measurable disease as defined by any of the following:
 - Serum monoclonal paraprotein (M-protein) level ≥ 1.0 g/dL (except for IgA subtype: ≥ 0.5 g/dL) or urine M-protein level ≥ 200 mg/24 hours; or

Health Data Specialists	
DARE (EAE-2017/MM02)- Statistical Analysis Plan	Version: 1.0 EN
Author: GC, Reviewer: MS, Quality Assurance: GK	Date: 02-02-2018

- Light chain multiple myeloma: Serum immunoglobulin free light chain ≥ 10 mg/dL and abnormal serum immunoglobulin kappa lambda free-light-chain ratio.

5. An eGFR < 30 ml/min/1.73 m² (CKD-EPI formula) or in need for dialysis
6. Eastern Cooperative Oncology Group performance-status score of 2 or less
7. Life expectancy of at least 3 months
8. Women of childbearing potential (WOCBP) must have two negative serum or urine pregnancy tests, one 10-14 days prior to start of the study drugs and one within 24 hours prior to the start of study drugs. Women must not be breastfeeding. WOCBP must agree to follow instructions for methods of contraception for 4 weeks before the start of treatment with study drugs, for the duration of treatment with study drugs, and for a total of 3 months after cessation of daratumumab treatment. Males who are sexually active with WOCBP must always use a latex or synthetic condom during any sexual contact with females of reproductive potential, even if they have undergone a successful vasectomy.

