6.5.4 Subgroups

In this study, no sub group analysis was planned to be performed within the primary and secondary endpoints analysis. However, it is considered necessary to further examine the data that will be collected, in order to provide insights for this non-in depth investigated population. Hence, additional subgroup and exploratory analyses will be performed (see 6.6). The following subgroups will be used for the additional analyses:

- ISS stage at the time of diagnosis
- Revised ISS stage at the time of diagnosis
- eGFR (< 15 vs ≥ 15 at baseline)
- Patients with at least one eGFR>30 measurement over the whole observation period vs patient without such a measurement
- ECG (normal vs at least one abnormality)
- Prior treatments (2-5 treatments vs >5 treatments)
- LDH ()
- FISH risk (low risk, standard risk, intermediate risk & high risk) (1)
- Age at diagnosis (<60 vs. ≥ 60).
- MRD negativity (negative vs. positive).

Health Data Specialists	
DARE (EAE-2017/MM02)- Statistical Analysis Plan	Version: 1.0 EN
Author: GC, Reviewer: MS, Quality Assurance: GK	Date: 02-02-2018

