6.6.1 Methods of Statistical Analyses

All data regarding patient demographics and baseline characteristics will be summarized on the FAS, overall, by means of summary descriptive statistics.

A complete description of patient disposition will be provided, specifying the number of enrolled patients, number of patients at each visit, completed and discontinued patients, and the reason for the discontinuation.

The analysis populations will be described and the reasons for excluding the patient from any analysis set will be provided with the number of protocol violators per each criterion.

Medical history data will be presented by MedDRA System Organ Class and Preferred Term.

Descriptive statistical analysis will be performed for all study data and epidemiological methods will be applied. Continuous variables will be summarized with the use of descriptive statistical measures [mean value, standard deviation (SD), median and range] (Table 2). Categorical/distinct variables will be displayed as frequency tables (N, %) (Table 3), by group.

Additional sub-group analyses will be performed. The basic demographic characteristics, the primary and the secondary endpoints will be summarized by group. Between groups comparisons will be performed. The sub groups that will be used are derived based on known risk factors that are associated either with the MM or with the RR. Hence, all the endpoints will be analyzed in the following subgroups:

Health Data Specialists	
DARE (EAE-2017/MM02)- Statistical Analysis Plan	Version: 1.0 EN
Author: GC, Reviewer: MS, Quality Assurance: GK	Date: 02-02-2018

- ISS stage at the time of diagnosis
- Revised ISS stage at the time of diagnosis
- ECG (normal vs at least one abnormality)
- Prior treatments (2-5 treatments vs >5 treatments)
- LDH ()
- FISH risk (low risk, standard risk, intermediate risk & high risk) (1)
- Age >60 vs ≤60
- MRD negativity (negative vs. positive).

Additional exploratory analyses will be performed, in order:

- To compare the PFS, the OS, the ORR and the number of prior treatments at baseline (2-5 treatments vs >5 treatments) between patients with eGFR < 15 vs ≥15 at baseline.
- To compare the PFS, the OS, the ORR and the number of prior treatments at baseline (2-5 treatments vs >5 treatments) between patients with at least one eGFR>30 measurement over the whole observation period vs patient without such a measurement

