- To compare the PFS, the OS, the ORR and the number of prior treatments at baseline (2-5 treatments vs >5 treatments) between patients with observed renal response and patients without renal response
- To evaluate if the FISH risk and renal response, measured as RRR are correlated.
- To evaluate if the FISH risk and renal response, using as cut-off point the eGFR>30, are correlated.
- To evaluate if the FISH risk and Prior treatments (2-5 treatments vs >5 treatments) are correlated

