APPENDIX 1) as their best overall response.

The response rate, along with its exact two-sided 95% CI, will be computed.

Renal Response Rate (RRR)

Rrr is defined as the proportion enrolled subjects who achieve a best response of renal partial renal response (PRRenal) or better using the criteria of the International Myeloma Working Group (IMWG) (APPENDIX 2).

Duration of Response (DoR)

DoR will be restricted to the subjects that achieve a best objective response of PR or better. It is measured from the time, in months, that the criteria for objective response are first met until the date of a progression event (according to the primary definition of PFS). A subject with objective response who does not have a progression event will be censored at the same time they were censored under the primary definition of PFS.

The DoR function will be estimated using the Kaplan-Meier product-limit method. Median and two-sided confidence intervals for median duration of response will be computed and Kaplan-Meier plots of DoR will be presented.

Time to Next Therapy (TNT)

TNT will be defined as the time, in months, from Cycle 1 Day 1 to the date to next anti-neoplastic therapy or death from any cause, whichever comes first. For subjects who neither start a new anti-neoplastic therapy nor die, survival time will be censored at the date of their last available follow-up assessment.

Time to next therapy will be calculated using a log-rank test procedure. The TNT function will be estimated using the Kaplan-Meier product-limit method. Median and two-sided confidence intervals for median TNT will be computed. Kaplan-Meier plots of TNT will be presented.

Overall Survival (OS)

Overall survival is defined as the time, in months, from the first dose of therapy to the date of death from any cause. If a patient is not known to have died, survival time will be censored at the date of last contact (“last known date alive”).

Overall survival will be estimated using the Kaplan-Meier product-limit method. Median and corresponding two-sided 95% confidence intervals will be computed. Kaplan-Meier plots of OS will be presented.

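### The SAP's exploratory eGFR>30 grouping starts where the entry limit ends and needs no confirmation, so it partly sorts patients by baseline eGFR

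*SAP*

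**What the plan says.** Entry (SAP 6.1.1, and inclusion criterion 7 in Protocol 5.1) requires "An eGFR < 30 ml/min/1.73 m² (CKD-EPI formula) or in need for dialysis".

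SAP 6.5.4 lists as a subgroup: "Patients with at least one eGFR>30 measurement over the whole observation period vs patient without such a measurement". SAP 6.6.1 repeats that grouping under "Additional exploratory analyses will be performed, in order" and uses it to compare PFS, OS, ORR and number of prior treatments. The same list adds "To evaluate if the FISH risk and renal response, using as cut-off point the eGFR>30, are correlated". That FISH line gives the cut-off but not the number of values or the time window. The single-value rule is the natural reading because the SAP offers no other, but it is not stated there.

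The secondary endpoint is separate. In SAP 6.6.1.4, RRR counts patients who "achieve a best response of renal partial renal response (PRRenal) or better" by the IMWG table in SAP Appendix 2.

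The protocol's rule on confirming response (section 7.1.1) relies on M-protein and does not cover eGFR.

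**The concern.** The entry limit and the grouping cut-off are the same number. A patient who enters at 28 needs only a small upward fluctuation to move into the >30 group, while a patient who enters at 10 must triple the value. Counting any single value over repeated visits gives the first patient many chances. Read literally, the whole observation period even includes the Cycle 1 Day 1 baseline value, which is measured after the screening value that established eligibility.

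At stake is how the exploratory results are read. A difference in PFS, OS or ORR between the groups could be taken as showing that renal improvement goes with better outcome, when part of it is a contrast between patients who entered just below 30 and patients who entered well below. In the FISH analysis, chance crossings dilute any true association. None of this depends on the separate timing problem of grouping patients by something seen after treatment starts.

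**Working it through.** **No figure to reproduce.** The documents state no misclassification rate, so the size must be built from assumptions.

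**Inputs from the documents.** Entry: eGFR <30. Group: at least one value >30. Scheduled values (Protocol Tables 7.1 and 7.2): weekly in cycles 1-2, which is 8 less Cycle 1 Day 1 = 7; every two weeks in cycles 3-6, which is 2 x 4 = 8. Total after baseline: 7 + 8 = 15.

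**Inputs assumed.** True eGFR constant within patient. Independent lognormal variation with CV 5%, 10% or 15%. One screening value <30. Non-dialysis patients only. Several baseline distributions.

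**Risk for one patient.** With sigma = sqrt(ln(1 + CV^2)), the chance that one value exceeds 30 is p = 1 - Phi(ln(30/true)/sigma). Over 15 values it is 1 - (1 - p)^15. At CV 10%:

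- true 20: p is about 0, giving about 0%
- true 25: p = 0.034, giving 40%
- true 26: p = 0.076, giving 69%
- true 27: p = 0.145, giving about 90%
- true 28: p = 0.245, giving about 98%

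The risk therefore sits almost wholly in patients entering in the mid to upper twenties.

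**Share of the non-dialysis cohort, by simulation with 15 values (%, at CV 5 / 10 / 15%).**

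| True eGFR | One value >30 | Two consecutive >30 |
|---|---|---|
| Uniform 5-30 | 8 / 16 / 22 | not tabulated |
| Uniform 10-30 | 10 / 20 / 29 | 4 / 8 / 11 |
| Uniform 5-34.5 | 10 / 19 / 27 | 5 / 10 / 14 |
| Uniform 10-34.5 | 13 / 24 / 34 | 7 / 13 / 18 |
| Normal, mean 15, SD 7 | 2 / 6 / 10-11 | from about 1 |

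The 34.5 rows admit patients whose true eGFR is a little above 30 but who screened low; these make up about a quarter of the crossers in those rows. The table spans roughly 2-34%. A case mix with nobody below 15 (uniform 15-30) would give 13 / 27 / 39%.

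Two refinements pull the figures down. Serial correlation of 0.8 between successive errors lowers the 34.5 rows to about 8-25%, and also makes a second consecutive value less informative. Dialysis patients who never exceed 30 scale everything by their share: at an assumed 30% dialysis, multiply by 0.7.

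**Who crosses.** In the tabulated settings, unchanged patients who cross have a mean baseline eGFR of about 25-29, against about 14-19 in those who do not.

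**Effect on the FISH contrast.** If a share f of unchanged patients crosses regardless of FISH risk, the proportion classed >30 is r + (1 - r)f. A true difference r1 - r2 then becomes (r1 - r2)(1 - f). With f = 0.20 it shrinks by 20%; with f = 0.02, by 2%.

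**Adding a 50% rise.** Requiring two consecutive values >30, each at least 1.5 times baseline, leaves 0-1% in the 34.5 rows. The rise is an extra hurdle only above a baseline of 20, since 1.5 x 20 = 30. At a baseline of 27 it asks for 40.5, and at 29 for 43.5.

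**The case against.** These analyses are exploratory, and with about 38 patients and four FISH categories an attenuation of this order is unlikely to change a conclusion. That stands, and it sets the priority.

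The size rests on inputs that the documents do not give. That also stands. A reader might infer that a fixed share of patients, say a tenth to a third, would be wrongly called recovered. The documents do not support this: the share could be near 2% if baseline eGFR centres on 15, it applies only to non-dialysis patients, and it is close to zero for true values of about 20 or less at CVs up to 10%. The SAP describes the group by its measurement and nowhere calls it recovered; only the FISH line uses the term renal response.

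The boundary at 30 is not peculiar to this grouping. IMWG minor response in SAP Table 7 runs from a baseline of 15-29 to a best value of 30-59, again without confirmation. True, but RRR does not count minor response.

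The SAP also runs stricter companions: comparisons by observed renal response, FISH against RRR, and baseline eGFR <15 versus >=15. These help a careful reader, but the last does not separate patients entering at 15-24 from those at 25-29, which is where chance crossing lies.

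A reader might also infer that the documents already supply the remedy, because Protocol Appendix 5 asks stage 4 patients to "increase their eGFR by at least 50% and improve to at least stage 3". They do not supply it cleanly. The same line prints a GFR of at least 60 beside stage 3, which is inconsistent with the stage 3 range of 30-59 given in the next line, and no planned analysis is assigned to the simplified criteria. Making the 50% rise the main definition is therefore debatable.

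**Conclusion.** The point holds for the exploratory eGFR>30 grouping. Applied as written, it admits unchanged patients who entered close to 30, so the PFS, OS, ORR, prior-treatment and FISH comparisons partly reflect baseline eGFR. Under assumed CVs of 5-15%, the false-crossing share among non-dialysis patients is roughly 2-34%: about 10-29% if true eGFR is uniform on 10-30, and about 2-10% if it centres on 15. The direction of the sorting was the same in every tabulated setting; only its size depends on the assumptions. What fraction of the >30 group would be false cannot be stated, because the true improvement rate is not given.

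A reader might extend this to the secondary endpoint. The documents do not support that: RRR asks for at least 30 from a baseline below 15, and at least 60 from a baseline of 15-29, both well clear of where the patient starts.

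This is a cheap improvement, not a flaw in the primary or secondary analyses.

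**What to change.** In SAP 6.5.4 and 6.6.1, define the group as eGFR >30 on two consecutive scheduled post-baseline assessments, excluding Cycle 1 Day 1. Use that one definition for the FISH correlation and for the PFS, OS, ORR and prior-treatment comparisons, and report baseline eGFR by group. With independent errors, confirmation removes about half or more of the false crossings.

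Because confirmation alone still leaves about 1-18% under the same assumptions, add a sensitivity analysis that also requires each of the two values to be at least 50% above the Cycle 1 Day 1 value (0-1% false crossings).

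The cost is SAP wording and a few lines of code. No new data are needed, since the values are already scheduled. The >30 group will be smaller. In the sensitivity analysis, true modest gains from a baseline above 20 are not counted: 27 to 35, for example, or 29 to anything under 43.5. The change does not cure the separate timing problem in comparing PFS and OS between groups formed after treatment starts.

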6.6.1.1 Patient-Reported Outcome (PRO) Measurements

No PROs will be used.

6.6.1.2 Statistical tests

Association between categorical variables will be assessed using either chi-square test (χ^2), Fisher exact test or McNemar test, as appropriate (Table 4). Furthermore, in order to examine the differences in the values of continuous variables at different time periods, Wilcoxon signed rank test for related samples and U-Mann Whitney test for independent samples will be used (Table 5).

Medical history and safety will be coded by MedDRA (the most updated version available) while System Organ Class (SOC) and Preferred Term (PT) will be tabulated in frequency tables (N, %).

Concomitant medication(s) will be coded through the ATC Drug Classification dictionary by WHO Collaborating Centre for Drug Statistics Methodology in terms of therapeutic subgroup, chemical subgroup and chemical substance and will be presented in frequency tables.

Health Data Specialists	
DARE (EAE-2017/MM02)- Statistical Analysis Plan	Version: 1.0 EN
Author: GC, Reviewer: MS, Quality Assurance: GK	Date: 02-02-2018

6.6.1.3 Primary Endpoint Analysis

The efficacy analysis will be performed based on the FAS as primary analysis and on the PPS as supportive analysis.

Progression Free Survival (PFS)

PFS is defined as the time, in months, from treatment initiation (Cycle 1 , day 1) to the date of the first documented tumor progression or death due to any cause, whichever comes first. Clinical deterioration will not be considered progression. For subjects who neither progress nor die, the survival time will be censored at the date of their last tumor assessment. For subjects who start a new anti-tumor treatment, survival time will be censored at the date of the start of the new treatment.

The PFS function will be estimated using the Kaplan-Meier product-limit method. Median and two-sided confidence intervals (CI) for median PFS will be computed by and Kaplan-Meier plots of PFS will be presented.

Absolute frequencies and proportions of patients with tumor progression or all-cause death will also be provided.

6.6.1.4 Secondary Endpoint Analysis

All secondary efficacy analyses will be performed based on the FAS.

Overall Response Rate (ORR)

ORR is defined as the proportion enrolled subjects who achieve a best response of partial response (PR) or better using the Modified criteria of the IMWG (

Rajan, A. M., and S. V. Rajkumar. "Interpretation of cytogenetic results in multiple myeloma for clinical practice." *Blood cancer journal* 5.10 (2015): e365.

Health Data Specialists	
DARE (EAE-2017/MM02)- Statistical Analysis Plan	Version: 1.0 EN
Author: GC, Reviewer: MS, Quality Assurance: GK	Date: 02-02-2018

APPENDIX 1) as their best overall response.

The response rate, along with its exact two-sided 95% CI, will be computed.

Renal Response Rate (RRR)

Rrr is defined as the proportion enrolled subjects who achieve a best response of renal partial renal response (PRRenal) or better using the criteria of the International Myeloma Working Group (IMWG) (APPENDIX 2).

Duration of Response (DoR)

DoR will be restricted to the subjects that achieve a best objective response of PR or better. It is measured from the time, in months, that the criteria for objective response are first met until the date of a progression event (according to the primary definition of PFS). A subject with objective response who does not have a progression event will be censored at the same time they were censored under the primary definition of PFS.

The DoR function will be estimated using the Kaplan-Meier product-limit method. Median and two-sided confidence intervals for median duration of response will be computed and Kaplan-Meier plots of DoR will be presented.

Time to Next Therapy (TNT)

TNT will be defined as the time, in months, from Cycle 1 Day 1 to the date to next anti-neoplastic therapy or death from any cause, whichever comes first. For subjects who neither start a new anti-neoplastic therapy nor die, survival time will be censored at the date of their last available follow-up assessment.

Time to next therapy will be calculated using a log-rank test procedure. The TNT function will be estimated using the Kaplan-Meier product-limit method. Median and two-sided confidence intervals for median TNT will be computed. Kaplan-Meier plots of TNT will be presented.

Overall Survival (OS)

Overall survival is defined as the time, in months, from the first dose of therapy to the date of death from any cause. If a patient is not known to have died, survival time will be censored at the date of last contact (“last known date alive”).

Overall survival will be estimated using the Kaplan-Meier product-limit method. Median and corresponding two-sided 95% confidence intervals will be computed. Kaplan-Meier plots of OS will be presented.

6.6.1.5 Safety Analysis

Safety analyses will be conducted on the Safety Set and will be reported.

Adverse events

AEs will be assessed according to the Common Terminology Criteria for AEs (CTCAE version 4.03).

Health Data Specialists	
DARE (EAE-2017/MM02)- Statistical Analysis Plan	Version: 1.0 EN
Author: GC, Reviewer: MS, Quality Assurance: GK	Date: 02-02-2018

The incidence of AEs will be tabulated by MedDRA System Organ Class and Preferred Term. The incidence of AEs will also be summarized by system organ class, preferred term and severity (based on CTCAE grades).

The same analysis will be repeated for SAEs regardless of drug relationship, for drug related SAEs, AEs with CTCAE grade 3 or 4 and for drug related AEs. AEs for which relationship to study drug is not specified will be considered treatment-related.

Deaths reportable as SAEs will be listed by patient and tabulated by type of AE.

Laboratory parameters

Categorization of laboratory values will be assigned programmatically as per NCI Common Terminology Criteria for Adverse Events (CTCAE) version 4.03 or according to normal ranges for those parameters without available CTCAE grading. The calculation of CTCAE grades will be purely based on the observed laboratory values, clinical assessments will not be taken into account.

CTCAE Grade 0 will be assigned for all non-missing values not graded as 1 or higher. Grade 5 will not be used.

For laboratory tests where grades are not defined by CTCAE v4.03, results will be graded by the low/normal/high (low and high) classifications based on laboratory normal ranges.

The following by-treatment summaries will be generated separately for hematology, biochemistry and urinary laboratory tests:

- Worst post-baseline CTCAE grade (regardless of the baseline status). Each patient will be counted only once for the worst grade observed post-baseline.
- Shift tables using CTCAE grades to compare baseline to the worst on-treatment value.
- Shift tables using the low/normal/high/ (low and high) classification to compare baseline to the worst on-treatment value, for laboratory tests where CTCAE grades are not defined.

Listings of all laboratory data with values flagged to show the corresponding CTCAE grades and the classifications relative to the laboratory normal ranges will also be generated.

Other safety data

ECGs, vital signs and ECOG PS will be listed and summarized.

ECG

- Shift table baseline to worst on-treatment result
- Listing of ECG evaluations for all patients with at least one abnormality
- Change from baseline QTcF

Vital signs

Health Data Specialists		
DARE (EAE-2017/MM02)- Statistical Analysis Plan	Version: 1.0 EN	
Author: GC, Reviewer: MS, Quality Assurance: GK	Date: 02-02-2018	

- Table with descriptive statistics at baseline, one or several post-baseline time points and change from baseline to this/these post-baseline time points

ECOG PS

- Shift tables comparing the baseline PS with the worst post-baseline result

